STUDY PROTOCOL

Purpose and Type of Research

The study was designed as a randomized controlled experimental research to determine the effects of reflexology applied to individuals who have suffered a stroke on pain levels, physiological parameters, and sleep quality. The study consists of an intervention group and a control group and aims to scientifically evaluate the place of reflexology within the holistic care approach.

Research Hypotheses

H0: Reflexology has no effect on pain in stroke patients.

H1: Reflexology has an effect on pain in stroke patients.

H0: Reflexology has no effect on arterial blood pressure in stroke patients.

H2: Reflexology has an effect on arterial blood pressure in stroke patients.

H0: Reflexology has no effect on pulse pressure in stroke patients.

H3: Reflexology has an effect on pulse pressure in stroke patients.

H0: Reflexology treatment has no effect on SPO2 in stroke patients.

H4: Reflexology treatment has an effect on SPO2 in stroke patients.

H0: Reflexology treatment has no effect on sleep quality in stroke patients.

H5: Reflexology treatment has an effect on sleep quality in stroke patients.

Location and Time of the Study

The study was conducted between October 15, 2024, and June 1, 2025, at the Physical Therapy and Rehabilitation Unit of Van Training and Research Hospital, Health Sciences University.

Research Population and Sample

The study sample consisted of stroke patients who met the inclusion and exclusion criteria. The sample selection was based on studies in the literature (Batvani et al., 2018; McFadden and Hernandez, 2010) and statistical consultation, the study power was calculated with the G* power analysis method at 80%, effect size 0.84, and 95% confidence interval. It was anticipated that a total of N=60 patients would be included, with n=30 patients in each group. Considering exclusion criteria and patient losses, the study was conducted with a total of N=70 patients, with n=35 patients in each group.

Inclusion Criteria

- Individuals over the age of 18,
- No diagnosis of any psychiatric illness or medication use,
- Hemiplegic stroke patients,
- Volunteering to participate in the study,
- According to the patient introduction form; patients describing hemiplegic shoulder pain and insomnia symptoms,
 - No history of neurological or psychiatric disorders other than stroke,
- No irritation or ulceration in the skin area where reflexology will be performed,
- No history of deep vein thrombosis,
- Able to speak and understand Turkish and able to read and write,
- Patients who voluntarily agree to participate in the study will be included.

Exclusion Criteria

- Refusal to participate in the study,
- Tetraplegic and paraplegic patients,
- Patients with stroke due to malignant brain damage undergoing chemotherapy or radiotherapy
- Those with mental and psychiatric disorders,
 - Those who have received professional massage therapy within the last month,
- Those with contraindications for foot massage and reflexology: those with generalized edema, pacemakers, heart attack, active gout, history of deep vein thrombosis, history of gallbladder and kidney stones, acute infection, fever, standing fracture, or wound will not be included in the study.

Randomization

The randomization process for the study was conducted using a computer-based random method. The randomization program available online at <http://www.randomization.com> was used to determine the groups. After defining the number of groups and participants in the study, this program randomly assigns participants to groups by generating a random number table.

Stroke patients who met the inclusion criteria and voluntarily agreed to participate in the study were assigned to the intervention (n=35) and control (n=35) groups according to the list generated by the program. The group distributions obtained as a result of randomization were kept confidential throughout the research process.

Form of Blinding in Research

Blinding is a control method that ensures participants do not know which group they belong to during the conduct and reporting of research. This method is applied to reduce the possibility of participants exhibiting biased attitudes and behaviors that could unknowingly influence the results. Blinding is one of the fundamental elements that increases the internal validity of randomized controlled trials (RCTs). As stated in the literature, only situations where participants' access to group information is restricted are defined as single blinding (Akin and Koçoğlu, 2017). In this study, the single blinding method was applied by keeping the information about which group the participants belonged to confidential.

Ethical Aspects of the Research

Prior to the research, ethical committee approvals were obtained from the "Hasan Kalyoncu University Health Sciences Non-Interventional Research Ethics Committee" (dated August 12, 2024, and numbered 2024/97). A work permit was obtained from the Van Provincial Health Directorate (dated October 3, 2024, and numbered E-50817530-770-255595908). During the study, the ethical principles outlined in the World Medical Association's Declaration of Helsinki were taken into consideration. Participants who voluntarily wished to participate in the study and who met the inclusion criteria were informed about the study and their informed consent

was obtained before they were assigned to the intervention and control groups. The necessary permissions were obtained from the authors of the scales used in the study.

Data Collection Tools

Data were collected using the Personal Information Form, Visual Analogue Scale (VAS), Richard-Campbell Sleep Scale (RCSS), and Physiological Parameters Recording Form.

Tools Used in Data Collection

The tools and equipment used in collecting research data and their purposes are detailed below:

- Digital blood pressure monitor: Used to measure participants' systolic and diastolic blood pressure.
- Pulse oximeter: Used to determine participants' oxygen saturation (SpO_2) and pulse rate levels.

Research Variables

Dependent Variables: Pain, Sleep Quality, and Physiological Parameters score averages are the dependent variables of the study.

Independent Variables: Reflexology application is the independent variable of the study.

Control Variables: Variables related to patients' socio-demographic and disease-related information are the control variables of the study.

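### Does raising the sample from 60 to 70 for exclusion criteria and losses mean that randomised patients will be removed from the comparison?

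*Protocol*

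**What the plan says.** The Protocol, under Research Population and Sample, opens with "The study sample consisted of stroke patients who met the inclusion and exclusion criteria". It then gives the sample size basis, "the study power was calculated with the G* power analysis method at 80%, effect size 0.84, and 95% confidence interval", and the resulting target: "It was anticipated that a total of N=60 patients would be included, with n=30 patients in each group". The final step reads "Considering exclusion criteria and patient losses, the study was conducted with a total of N=70 patients, with n=35 patients in each group". No rate is given for exclusions or for losses.

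Under Randomization the same 35 and 35 reappear as the assigned patients: "Stroke patients who met the inclusion criteria and voluntarily agreed to participate in the study were assigned to the intervention (n=35) and control (n=35". The list of contraindications under Exclusion Criteria ends with "acute infection, fever, standing fracture, or wound will not be included in the study". Ethical Aspects of the Research states that informed consent was obtained before assignment to the groups.

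**The concern.** When eligibility is settled before assignment, exclusion criteria determine how many patients must be screened. They cannot turn 70 randomised patients into 60. Naming them as a reason to randomise more therefore suggests that some patients might be taken out after assignment for meeting a criterion. Several listed conditions, such as fever, acute infection or a wound, can arise after entry. They might also be noticed more often in the group that receives reflexology.

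If patients who became unwell were dropped from one group and not from the other, the groups compared would no longer be the groups randomised, and the result could favour reflexology. A plan that provided for this would need correcting.

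**Working it through.** **1. The plan's own base figure.** Inputs from Research Population and Sample: power 80%, effect size 0.84, 95% confidence. Assumptions: 0.84 is a standardised mean difference, and the test is two-sided at alpha 0.05.

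- Normal approximation: n per group = 2 × (1.960 + 0.842)² / 0.84² = 2 × 7.85 / 0.7056 = 22.3, so 23. The two-sample t-test gives 23.2, so 24 per group and 48 in total.
- One-sided: 18 (normal) or 19 (t-test) per group.
- The stated 30 per group is not reproduced at 80% power. It corresponds to about 90% power two-sided (30 by the normal formula, 31 by the t-test). This is a separate matter, and it errs on the large side.

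**2. The step from 60 to 70.**

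- Allowance: 10/70 = 14.3% of those randomised, or 5 of 35 per group.
- With losses as the only reason: 60/(1 - 0.143) = 70.
- The protocol states no loss rate. For assumed rates, 60/(1 - d) gives 67 at 10%, 70 at 14.3%, 71 at 15% and 75 at 20%. The plan's 70 lies inside this range, so losses alone can explain it and no post-assignment exclusion is needed.

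**3. Where the text places eligibility.**

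| Protocol section | What it fixes |
|---|---|
| Research Population and Sample | The sample had met both inclusion and exclusion criteria |
| Exclusion Criteria | Contraindicated patients do not enter the study |
| Randomization | Eligible, consenting patients are the ones assigned, 35 and 35 |
| Ethical Aspects of the Research | Consent comes before assignment |

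None of these removes a patient after assignment. The inflation sentence gives no timing for exclusions, so it does not contradict the other sections. Refusal is listed as refusal to take part, which is an entry condition; a later withdrawal is a patient loss.

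**4. Size of the feared bias.** Suppose all five allowance patients are removed from one group only, and are 0.5 to 1.0 SD worse than the other 30. That group's mean shifts by (5/35) × 0.5 = 0.07 SD to (5/35) × 1.0 = 0.14 SD. This is 8.5% to 17% of the planned effect of 0.84, or about 10% to 19% of the 0.74 SD that 30 per group detects with 80% power. The arithmetic is correct, but every input is assumed. The whole allowance goes to exclusions and none to losses, removal is confined to one group although the allowance is equal in both, and the 0.5 to 1.0 SD has no source in the protocol. With the same removal in both groups the shifts cancel and the difference in means does not move.

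**5. Power if the plan is followed.** Two-sided t-test at effect size 0.84:

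| Patients with outcome data | Power |
|---|---|
| 70 (no loss) | 93% |
| 60 (14.3% loss) | 89% |
| 56 (20% loss) | 87% |
| 49 (30% loss) | 82% |

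**The case for a change.** The strongest argument for the concern is that the Randomization section conditions assignment on the inclusion criteria and agreement, and does not mention the exclusion criteria there. Combined with a sample size that sets randomised patients aside for exclusions, this could leave room for taking an assigned patient out when a contraindication comes to light. The contraindications are specific to foot massage and reflexology, so there would be more reason to look for them in the intervention group. No analysis plan is at hand to rule this out.

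Part of this stands. Exclusion criteria are not a proper reason for enlarging the number randomised, and the protocol does not say how the ten extra patients divide between exclusions and losses.

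The rest does not follow. Research Population and Sample says that the sample had met both sets of criteria, and the exclusion list is itself worded as a bar to entry. Nothing in the protocol describes checks after assignment that differ by group, so unequal detection is conjecture. A loose phrase that runs together recruitment shortfall and attrition explains the sentence equally well and fits the other sections better. Which patients are analysed, and how missing outcomes are handled, is commonly laid down in a statistical analysis plan. Its absence from the material at hand does not show that patients will be dropped.

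**Conclusion.** The concern does not hold. The protocol neither states nor requires the removal of randomised patients, and its sections do not conflict on when exclusions act. The allowance of ten patients equals a 14.3% loss rate, and patient losses are among the reasons the protocol gives for it. Followed as written, the plan randomises 70 eligible patients and keeps power above 80% even with 30% loss, taking 0.84 as a standardised mean difference tested two-sided at 5%. The shift of 0.07 to 0.14 SD arises only under a one-sided removal that the protocol does not describe. The mention of exclusion criteria in the allowance is imprecise, but correcting it would change neither the sample size nor any result. The conclusion rests on the protocol text alone; an analysis plan that did provide for dropping assigned patients would be a different matter.

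### Confidentiality of group information is the only means given for participant blinding, and it cannot hide whether reflexology was received

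*Protocol*

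**What the plan says.** The section Form of Blinding in Research sets its own standard: "Blinding is a control method that ensures participants do not know which group they belong to during the conduct and reporting of research". It gives the purpose as well: "This method is applied to reduce the possibility of participants exhibiting biased attitudes and behaviors that could unknowingly influence the results". Citing the literature, it adds that "only situations where participants' access to group information is restricted are defined as single blinding". It then states how this was done: "In this study, the single blinding method was applied by keeping the information about which group the participants belonged to confidential".

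The Randomization section adds only this: "The group distributions obtained as a result of randomization were kept confidential throughout the research process".

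On the treatments, Purpose and Type of Research says: "The study consists of an intervention group and a control group". The protocol does not say what the control group received. That reflexology involves physical contact is shown by an inclusion criterion, "No irritation or ulceration in the skin area where reflexology will be performed", and by the exclusion criteria, which list contraindications to foot massage and reflexology together.

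**The concern.** Secrecy about an allocation list and a patient's unawareness of treatment are different things. The first can protect the assignment process. The second requires that patients in both groups have experiences they cannot tell apart. The protocol describes the first and claims the second.

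Two of the five hypotheses depend on it. Pain is measured by VAS (H1) and sleep quality by the Richard-Campbell scale (H5). If patients knew whether they had been treated, expectation and the attention that comes with treatment could shift both scores without any specific effect of reflexology. A reader of the protocol is told that blinding reduced this bias, and would give the pain and sleep results more credit than the described design supports. Blood pressure, pulse pressure and SpO2 (H2 to H4) rest on device readings, where reporting bias is less direct, so the point is confined to H1 and H5.

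**Working it through.** The point is one of design logic, and the protocol gives no figure to reproduce. The statements are therefore set side by side first.

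1. **Property claimed:** participants do not know their group (Form of Blinding in Research).
2. **Means stated:** group information is kept confidential (same section), and the group distributions are kept confidential (Randomization).
3. **Nature of the treatment:** it is performed on an area of the patient's skin (Inclusion Criteria), with foot-massage contraindications (Exclusion Criteria). It is perceptible to the person receiving it.
4. **What patients knew beforehand:** they were informed about the study and consented before assignment (Ethical Aspects of the Research).
5. **What would make the claim true:** a control contact that patients could not distinguish from reflexology. The protocol mentions no sham, placebo touch or attention control.

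Item 2 yields item 1 only if item 5 was in place. The text does not describe item 5, so the stated mechanism does not by itself produce the stated property.

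**Illustration of what is at stake.** The bias is unknown, so a shift *b*, in SD units, is assumed.

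- Inputs: 35 per group (Research Population and Sample), all assumed evaluable; a two-sample t test, two-sided at 5% (assumed); no true effect.
- Degrees of freedom: 35 + 35 − 2 = 68.
- Noncentrality: *b* × √(35/2) = *b* × 4.183.

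| Assumed shift *b* (SD) | Noncentrality | Probability of rejection |
|---|---|---|
| 0 | 0 | 5.0% |
| 0.1 | 0.418 | 7.0% |
| 0.2 | 0.837 | 13.1% |
| 0.3 | 1.255 | 23.6% |
| 0.4 | 1.673 | 37.8% |
| 0.5 | 2.092 | 54.1% |

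With 30 evaluable per group the rates are slightly lower: 6.7%, 11.9%, 20.8% and 47.8% at shifts of 0.1, 0.2, 0.3 and 0.5 SD.

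For scale, the smallest observed difference that reaches significance with 35 per group is t(0.975; 68) × √(2/35) = 1.995 × 0.239 = 0.477 SD. Against the planning effect of 0.84 this is 0.477 / 0.84 = 0.57. A result well short of the planned effect would therefore be declared significant, and reporting bias could supply part of it.

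**The case against.** The strongest reply is that the document says little about procedures at all. It gives no technique, no number or length of sessions, and no control procedure. Silence about a sham is part of that general silence and is not evidence that none was used. If control patients received contact they could not tell from reflexology, withholding the group label would be a workable way to blind them and the blinding statement would be true. This stands as a limit: it cannot be said that patients were in fact unblinded. It does not rescue the text, which credits the blinding to confidentiality and names nothing that would make confidentiality sufficient.

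A second reply is that the protocol meets the looser definition it cites, which asks only that access to group information be restricted. But experiencing the treatment gives that access, and the section's opening sentence demands more: that participants do not know their group.

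Third, the protocol names the VAS and the sleep scale without saying who completes them. That both are patient-rated is an inference, though a reasonable one given that the inclusion criteria require literacy and rely on patients describing their own pain and insomnia.

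Fourth, the rejection rates say nothing about the bias in this trial. That is correct: they show sensitivity to an assumed shift, and the conclusion does not rest on them.

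Finally, the study is described as completed and an open comparison can still be informative. Both are true. They bear on the remedy, which is a correction of description and interpretation, and not on whether the claim is supported.

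**Conclusion.** The concern holds, and the blinding statement should be corrected. The protocol makes an affirmative claim about validity and supports it with a mechanism that cannot deliver it for a perceptible physical treatment unless an indistinguishable control contact was used, and none is described. Two of five hypotheses are affected, H1 and H5.

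The size of any bias is unknown. Under assumed shifts of 0.1 to 0.5 SD, the false-rejection rate at 35 per group would run from 7.0% to 54.1% in place of 5%. Confidence is high that the stated mechanism is inadequate. No conclusion is drawn about what patients actually knew.

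**What to change.** First, state what the control group received. The wording then follows from that.

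- **If it was a sham contact that patients could not distinguish from reflexology:** describe it, name it as the method of blinding in place of confidentiality, and keep the single-blind label.
- **If it was not:** withdraw the single-blind claim and state that participants were not blinded. Interpret H1 and H5 as comparing reflexology as delivered, including attention and expectation, with the control condition.

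The statement about confidential group distributions can stay in the Randomization section, but it should not serve as evidence of participant blinding.

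The cost is one description of the control condition and a rewording of the blinding section. If no sham was used, the trial carries a less favourable blinding statement and a narrower reading of the pain and sleep results. Sample size, staffing and procedures do not change.

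### Do the protocol's control variables shut out adjustment for the baseline value of each outcome?

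*Protocol*

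**What the plan says.** The Research Variables section of the protocol has three one-line entries.

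- **Dependent:** "Pain, Sleep Quality, and Physiological Parameters score averages are the dependent variables of the study".
- **Independent:** the reflexology application.
- **Control:** variables on "socio-demographic and disease-related information are the control variables of the study".

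The section stops there. The protocol gives no analysis model, no covariate list for a model, no measurement times, and no statement of how the control variables are to be used.

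Two other places bear on the point. Under Inclusion Criteria, the protocol admits "patients describing hemiplegic shoulder pain and insomnia symptoms", judged from the patient introduction form and with no severity limit. Under Randomization, it describes a computer-generated list and mentions no stratification.

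The sample-size paragraph states that "the study power was calculated with the G* power analysis method at 80%, effect size 0.84, and 95% confidence interval". It arrives at 30 patients per group, raised to 35 per group for exclusions and losses.

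**The concern.** The protocol does say which variables are controlled, and pre-treatment pain, sleep quality, blood pressure, pulse and SpO2 are not named among them. Read as the adjustment set, the entry would be a poor one. It would be open-ended, covering any socio-demographic or disease variable, and it would omit the covariate that usually predicts each outcome best.

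Two things would then be at stake.

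- **Precision.** Between-patient variation that baseline could explain would stay in the error term.
- **Chance imbalance.** Patients enter with pain and insomnia of any severity, and groups of this size can differ at baseline by luck. Adjustment for baseline removes the effect of such a gap from the estimate and introduces no bias under randomisation.

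**Working it through.** **1. What the sentence fixes.** The concern needs the control entry to be an exclusive list of model covariates. The text does not make it one.

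- No word limits the list to the variables named.
- No model is named for these variables to enter.
- A pre-treatment VAS or sleep score is a measurement of a dependent variable. Its absence from the control line therefore does not show whether it enters the analysis.
- Disease-related information is not defined. The patient introduction form already captures shoulder pain and insomnia symptoms, so baseline symptom data could fall within it.

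The sentence is thus compatible with analysis of covariance on baseline, with change scores and with a repeated-measures model. What is left is that the protocol does not mention baseline adjustment. That is a detail commonly settled in the statistical analysis plan.

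**2. The plan's own sample-size figure.** Inputs from the protocol are an effect size of 0.84, 80% power and 95% confidence. Assumptions are that 0.84 is Cohen's d and that the test is a two-sided two-sample t test at 0.05.

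- Normal approximation: n per group = 2 × (1.960 + 0.842)² / 0.84² = 15.70 / 0.7056 = 22.2, so 23.
- Noncentral t: 23.2, so 24 per group, or 48 in total.

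The stated 30 per group is not reproduced, but it errs on the large side. This is a separate matter and does not affect the present point.

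**3. What adjustment would add at the stated effect size.** The protocol gives no baseline–outcome correlation ρ, so 0.3, 0.5 and 0.7 are assumed. Adjusting for baseline multiplies the error variance by 1 − ρ², so the effective standardised difference becomes 0.84 / √(1 − ρ²). Power is from the noncentral t.

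| ρ | 1 − ρ² | Variance removed | Power, 30 per group | Power, 35 per group |
|---|---|---|---|---|
| no adjustment | 1.00 | 0% | 89.2% | 93.4% |
| 0.3 | 0.91 | 9% | 91.8% | 95.3% |
| 0.5 | 0.75 | 25% | 95.9% | 97.9% |
| 0.7 | 0.51 | 49% | 99.4% | 99.8% |

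At 35 per group the gain is about 2 to 6 percentage points. At 30 per group it is about 3 to 10.

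**4. A smaller true effect.** At d = 0.6 with 30 per group, power goes from 62.8% unadjusted to 66.8%, 75.1% or 89.2% at ρ = 0.3, 0.5 or 0.7. The arithmetic is right, but d = 0.6 is not a figure in the protocol. The largest gain also needs the highest assumed ρ.

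**5. The comparator.** These gains are measured against an analysis of post-treatment values alone, which the protocol does not specify. In terms of extra patients, 1/(1 − ρ²) − 1 gives 10%, 33% and 96%. Against a change-score analysis, which the text equally allows, the variance ratio is (1 − ρ²) / [2(1 − ρ)] = (1 + ρ)/2, that is 0.65, 0.75 and 0.85. The equivalent gains are then 54%, 33% and 18%. If the analysis already adjusts for baseline, the gain is nil. The loss cannot be sized without knowing the method it is measured against.

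**The case for a change.** The strongest reply is that the protocol is not silent. It has an entry for control variables, fills it with a wide class, and leaves out the values that matter most. An analyst could follow that entry, pick weak predictors after seeing the data, and never adjust for baseline pain or sleep.

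Nor does the imbalance argument depend on the effect size. At 35 per group the standard error of a standardised baseline difference is √(2/35) = 0.24, so a gap of at least 0.25 SD in a given outcome arises by chance in about 30% of trials. At 30 per group the figures are √(2/30) = 0.26 and about 33%.

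Part of this stands. Baseline adjustment is good practice in a trial of this size, the class of control variables is loosely worded, and chance imbalance is a real possibility. But it shows only that the entry would be a weak adjustment set if it were one, and nothing in the section gives it that function. The possible imbalance is likewise a reason to adjust in the analysis, and the protocol does not rule that out.

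The remedy would also rest on something unseen, because the protocol does not state that the outcomes were measured before treatment. And since the document reports the study as already conducted, a covariate set redefined now would have to be declared post hoc unless it could be shown to predate the analysis.

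**Conclusion.** The concern does not hold. The control-variable entry classifies variables. It does not specify covariates, and it does not exclude the baseline value of any outcome. Without that exclusion, what remains is a missing analysis detail of the kind a statistical analysis plan normally supplies, so it is not an error in this protocol. At most one could ask the sponsor whether the entry is meant as the adjustment set.

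On the protocol's own effect size the stake is limited: unadjusted power is about 89% at 30 per group and 93% at 35, and adjustment adds about 2 to 6 percentage points at 35. These figures assume that 0.84 is a standardised mean difference, that the test is two-sided at 0.05, that the baseline–outcome correlation lies between 0.3 and 0.7, and that the alternative is a comparison of post-treatment values alone. A smaller true effect would raise the stake, but it would not turn the sentence into a restriction.
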